3.1.7 Assessment subset 7: Sensory system evaluation

In this session important deficits in vision and hearing are recorded. The evaluation is based in questioning the participants themselves and the clinical impression of the examiner during the visit. The evaluation refers to any remaining deficit after correction with glasses or hearing aid. Table 10 displays this subset of the battery.

Table 10. SENSORY SYSTEM EVALUATION

Vision	Question to the participant AND clinical evaluation/impression Choose the one that applies
	 Sees well Sees moderately Sees poorly
Hearing	 Question to the participant AND clinical evaluation/impression Choose the one that applies 1. Hears well 2. Hears moderately 3. Hears poorly

3.1.8 Assessment subset 8: Nutritional assessment

Weight loss and sarcopenia are key components to frailty. Due to various factors, older adults are at high risk for malnutrition which is related to frailty itself (12) and leads to muscle mass loss, reduced functionality, adverse health outcomes and complications and premature death (13, 14, 15).

The Mini Nutritional Assessment (MNA) is a simple tool, translated into more than 20 languages, useful in clinical practice to measure nutritional status in elderly persons. It is a well-validated tool, with high sensitivity, specificity, and reliability. An MNA score > or = 24

identifies patients with a good nutritional status. Scores between 17 and 23.5 identify patients at risk for malnutrition (16).

A short screening version (MNA-SF) has been developed (17), which, if positive, indicates the need to complete the full MNA.

In our study we are going to use the short form as a screening tool and if it gives us a score lower than 11, then the long version is applied. It takes less than 4 minutes to administer the MNA-SF and between 10 and 15 minutes for the full MNA. Table 11 summarizes this subset of the clinical evaluation and annex 5 presents the questionnaire in its original form. Translations in both French and Greek are available in the official questionnaire's web site (18).

Table 11. NUTRITIONAL ASSESSEMENT

Nutritional state	MNA short form scale for nutritional problem detection	
	If score \leq 11 in short form, then application of the full questionnaire.	
	(Annex 5)	
	MNA extended version	
	To be applied only if detection score ≤11	
	(Annex 5)	

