APPENDIX I- Clinical Frailty Index (CIFI)

We define loss of physiological reserve changes in ten domains investigated by the clinical evaluation assessment (health status, physical performance, nutritional, cognitive, psychological, wellness etc). We add up scores from all variables in order to have an initial rough index that expresses frailty parameters altogether. Due to lack of sufficient data in the literature about the specific weight of each item and even of each domain, we have chosen to initially take equal weights for each item, aiming at validating our model in the end of the study in terms of frailty evolution predictive value, as expressed by outcomes occurrence.

Items that will contribute to the generation of the CIFI are listed in table 22.

Table 22. Components of Clinical Frailty Index

Items	
Medical Domain (M)	Each polypathology /Comorbidities (M)
	Comorbidity's impact (M, P, s, c)
	Polymedication (M, p, c)
	Orthostatic hypotension (M, p)
	Visual impairment (M, S, p)
	Hearing impairment (m, S, c)
General Condition	Unintentional weight loss (M, ψ)
Domain (Μ, ψ)	Self-reported exhaustion (M, ψ)
Physical Condition	Balance (single foot standing) (P, m)
(P, m, c)	Gait-related task speed* (P, c)
	(Timed Get Up and Go test)
	Gait - speed 4 m (P, m)
	Lower limb strength (P, m)
	Grip strength –dynamometer (P, m)
	Qualitative evaluation of mobility (P, m)
	Low physical activity (P, M, s, ψ)
Nutrition (M, Ψ , c, s)	Too low BMI (Μ, Ψ, p, c, s)
	Too high BMI (M, Ψ, Ρ, ϲ, s)
	Waist circumference (M, Ψ , P, c, s)
	Lean body mass (M, P, ψ)
	Total MNA score (M, Ψ, p, c, s)
Cognitive Domain	MMSE scores (C, ψ , m)
(C, ψ, m, s)	MoCA score(C, ψ, m)
	Subjective memory complaint(C, ψ , m, s)
	Natural language analysis (C, Ψ)
Psychological Domain	GDS-15*(Ψ, S, c)
(Ψ, S, c)	Self-rated anxiety (Ψ, S, c)
	Natural language analysis (C, Ψ)
Social Domain (S, Ψ , m)	Living conditions (S, Ψ , p, m)

Social Domain (S, Ψ, m)	Leisure activities (S, Ψ , p, m)			
	Membership of a club (S, Ψ , p, m)			
	Number of visits and social interactions per week (S, Ψ , p, m)			
	Number of telephone calls exchanged per week (S, ψ , m)			
	Approximate time spent on phone per week (S, ψ , m)			
	Approximate time spent on videoconference per week (S, ψ)			
	Number of written messages sent by the participant per week (S, ψ , m, p)			
Environmental Domain	Subjective suitability of the housing environment according to			
(S, P, m)	participant's evaluation (S, P, m)			

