	Subjective suitability of the housing environment according to			
	investigator's evaluation (S, P, m)			
	Number of steps to access house (S, P, m)			
Wellness (Ψ, S, M, P, c)	Quality of life self-rating (Ψ, S, M, P, c)			
	Self-rated health status (M, Ψ)			
	Self-assessed change since last year (M, ψ)			
	Self-rated anxiety (Ψ, S, M, P, c)			
	Self-rated pain (M, P, ψ)			
Lifestyle (Ρ, Μ, ψ,s)	Smoking (Μ, Ψ, p, s)			
	Alcohol (Μ, Ψ, S)			
	Physical Activity (P, M, ψ,s)			
Tags (reflecting impact of	of each item on CIFI)			
Physical: P dominant, p recessive				
Medical: M dominant, m recessive				
Social: S dominant, s recessive				
Cognitive: C dominant, c recessive				
Psychological: Ψ dominant, ψ recessive				

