Annex 4- alcohol units' equivalences

Annex 5- Mini Nutritional Assessment

Mini Nutritional Assessment **MNA**[®]

Last name:	e: First name:			
Sex	Age:	Weight, kg:	Height, cm:	Date:
	by filling in the boxes with the a ne screen. If score is 11 or less		sessment to gain a Malnutrition Indicate	or Score.
creening			J How many full meals does the 0 = 1 meal	e patient eat daily?
	declined over the past 3 mo stive problems, chewing or s		1 = 2 meals 2 = 3 meals	
0 = severe decre	ase in food intake crease in food intake in food intake		 K Selected consumption market At least one serving of dairy pr (milk, cheese, yoghurt) per day Two or more servings of legum 	oducts y yes no [
0 = weight loss gr 1 = does not know	etween 1 and 3kg (2.2 and 6.6	bs)	or eggs per week • Meat, fish or poultry every day 0.0 = if 0 or 1 yes 0.5 = if 2 yes 1.0 = if 3 yes	yes 🗌 no [
Mobility 0 = bed or chair b 1 = able to get ou 2 = goes out	ound t of bed / chair but does not go	out	L Consumes two or more servi per day? 0 = no 1 = yes M How much fluid (water, juice,	
past 3 months?	ychological stress or acute d 2 = no	isease in the	consumed per day? 0.0 = less than 3 cups 0.5 = 3 to 5 cups 1.0 = more than 5 cups	□.
Neuropsycholog 0 = severe dementia 1 = mild dementia 2 = no psycholog	ntia or depression		N Mode of feeding 0 = unable to eat without assist 1 = self-fed with some difficulty 2 = self-fed without any probler	
Body Mass Index 0 = BMI less than 1 = BMI 19 to less 2 = BMI 21 to less 3 = BMI 23 or gre	s than 21 s than 23	it in m) ²	O Self view of nutritional status 0 = views self as being malnou 1 = is uncertain of nutritional st 2 = views self as having no nut	rished ate ritional problem
2-14 points: -11 points:	ubtotal max. 14 points) Normal nutritional status At risk of malnutrition Malnourished		P In comparison with other per the patient consider his / her 0.0 = not as good 0.5 = does not know 1.0 = as good 2.0 = better	
or a more in-depth	assessment, continue with que	stions G-R	Q Mid-arm circumference (MAC) in cm

Assessment

G Lives inde	pendently (not in nur	sing home or hospit	al)
1 = yes	0 = no		
H Takes mor	e than 3 prescription	drugs per day	
0 = yes	1 = no		

н	H Takes more than 3 prescription drugs per day		
	0 = yes	1 = no	
	-		

IPressure sores or skin ulcers0 = yes1 = no

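### The Clinical Frailty Index sums a total MNA score that is collected only after a positive short-form screen, and lists self-rated anxiety and natural language analysis twice under an equal-weight rule

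*Protocol*

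**What the plan says.** **Who has a full MNA.** Table 11 (section 3.1.8) restricts the extended form: "To be applied only if detection score ≤11". The form in Annex 5 agrees ("If score is 11 or less"). The running text of section 3.1.8 differs: "if it gives us a score lower than 11, then the long version is applied".

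**How totals are read.** Section 3.1.8 gives cut-offs on the 30-point scale. "An MNA score > or = 24" marks good nutritional status, and "Scores between 17 and 23.5 identify patients at risk for malnutrition".

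**What the index uses.** Table 22 lists "Total MNA score" in the Nutrition domain, with no separate entry or value for people who had only the short form. Appendix I adds up the scores of all variables and says of the weights: "we have chosen to initially take equal weights for each item". It calls the index initial and rough, to be validated at the end of the study.

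**Repeated entries.** Table 22 lists self-rated anxiety under Psychological (three tags) and again under Wellness (five tags). The self-evaluation battery in Table 14 has one anxiety scale. Natural language analysis is listed under Cognitive and under Psychological with identical tags.

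**Where the index goes.** Section 5.1 computes CIFI at every clinical evaluation and adds it to the Technical Frailty Index to form the Combined Frailty Index. Section 5.2.3 names differences in these indices as measured changes. Table 24 uses CIFI directly for MO1 and MO2.

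**The concern.** An additive index needs a value for every component in every person. Here one component is unobserved by design in everyone who passes the nutrition screen. An analysis plan could assign those people a code, but it could not recover a total that was never collected. Because a person can cross the screening threshold between evaluations, the item can also enter or leave that person's index, and part of an index difference could then reflect which form was used.

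The repeats conflict with the equal-weight rule if Table 22 is summed as printed. The conflicting triggers could lead the three centres to collect different data from participants who score exactly 11.

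**Working it through.** The protocol states no figure to reproduce. The check is score-range arithmetic on Annex 5 and a count of Table 22.

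**1. Which totals can be observed.** Annex 5 gives a screening maximum of 14 and an assessment maximum of 16, so 14 + 16 = 30.
- Screen-positive (11 or less): the total runs from 0 to 11 + 16 = 27. Under the text's rule (below 11) the maximum is 10 + 16 = 26.
- Screen-negative (12 to 14): no total is collected. Had the full form been given, it would lie between 12 + 0 = 12 and 14 + 16 = 30. Totals above 27 can therefore never be observed.

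**2. What a screen-negative could receive in the sum.**

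| Handling | Result |
|---|---|
| Short-form points entered beside 30-point totals | 12–14 falls below the at-risk band of 17–23.5. The gap runs from 17 − 14 = 3 to 23.5 − 12 = 11.5 points, in the wrong order |
| Left missing and imputed under 5.4.1 | Models are learned from available complete data, but totals are observed only in screen-positives |
| Coded as normal | No reversal and no imputation |

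The protocol states none of the three.

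**3. Change over time.** A participant who screens at 11 at one evaluation and 12 at the next has a total at the first and none at the second. The short-form change is 1 point. The change in the CIFI item depends on which row above applies.

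**4. Weights.** Table 22 entries by domain, in order: 6 + 2 + 7 + 5 + 4 + 3 + 8 + 3 + 5 + 3 = 46.
- Item listed once: 1/46 = 2.17%.
- Anxiety or language analysis, summed as printed: 2/46 = 4.35% each, 4/46 = 8.70% together.
- Each counted once: 46 − 2 = 44 entries, 1/44 = 2.27% each, 2/44 = 4.55% together.

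These shares assume that the comorbidity line is one entry. If each condition counts separately, all shares fall, but the 2-to-1 ratio stays.

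**5. Extent.** One MNA entry plus four repeated listings gives 5 of 46 entries (10.9%).

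**6. Trigger.** At a short-form score of exactly 11, Table 11 and Annex 5 call for the full form and the text of 3.1.8 does not.

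**The case against.** A reader might infer that CIFI necessarily ranks well-nourished people below those at risk. The documents do not support that. No section says that short-form points share a variable with 30-point totals. Several Table 22 entries are worded as deficits, such as BMI too low or too high, which suggests a per-item coding that an analysis plan may supply. Coding screen-negatives as normal removes the reversal.

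Nor do observed totals come only from poorly nourished people. A screen-positive can reach 24 to 27, which section 3.1.8 classes as good nutritional status. The 3 to 11.5 point range also leaves out screen-positives whose totals are below 17.

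The repeats can be read more kindly too. The two anxiety entries carry different tags and may be a cross-listing. Natural language analysis produces several outputs (section 3.2.1), so its two listings could stand for different metrics. Sections 5.4.2 and 5.4.3 plan to combine equivalent variables and remove overlapping observations. The weights are called initial, and the nutritional proxy outcome in section 5.2.2 is weight loss, not the MNA.

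All of this limits the size of the problem. It does not supply the missing total, say whether a repeat is summed once, or settle a score of exactly 11. The plans for overlapping variables do not change the sum that Appendix I defines.

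**Conclusion.** The point holds as an inconsistency between what the index sums and what the protocol collects. The MNA total is absent by design for screening scores of 12 to 14 and can come and go between evaluations. Reversal, or imputation from screen-positives alone, is a possible consequence that depends on unstated coding; neither is established.

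The doubled weight (4.35% against 2.17%) rests on summing Table 22 literally. It is firmer for anxiety, which comes from one scale, than for language analysis. The contradiction at a score of exactly 11 needs no assumption. The reach is five of 46 listed entries in an index described as initial and rough. The effect on any study conclusion cannot be sized from the document. The changes should be made because they are cheap and the index feeds the combined index and the change measures.

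**What to change.** - In Table 22, replace the MNA total with the short-form score (0 to 14), which the protocol collects from every participant at each clinical evaluation. Score it so that higher means worse. Keep the full MNA as a descriptive measure in screen-positives.
- Sum self-rated anxiety once. Sum natural language analysis once, unless a distinct metric is named for each domain.
- Reconcile the full-MNA trigger in the text of section 3.1.8 with Table 11 and Annex 5.

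**Cost.** Table and text edits and a scoring change; no new data. The index loses the detail of the full form. Overlap with other items also grows: BMI and weight loss, already separate CIFI entries, supply up to 3 points each, which is 6/30 = 20% of the full MNA but 6/14 = 43% of the short form. If the full total is kept for that reason, the protocol should at least state the value that a screen-negative receives.

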3.1.9 Assessment subset 9: Activities of daily living

The evaluation of the activities of daily living is of great importance when assessing an older adult, since it primarily reflects the level of autonomy of a person.

- Activities of daily living (ADL). The Katz Index of ADL (19) refers to performance in the six basic functions of bathing, dressing, toileting, transferring, continence, and feeding. Although no formal reliability and validity reports could be found in the literature, the tool is used extensively as a flag signalling functional capabilities of older adults in clinical and home environments (20).
- Instrumental ADL (IADL). The tool that is going to be used is the Lawton's IADL scale which is an appropriate instrument to assess independent living skills (21), more complex than basic self-care activities. The domains that are evaluated by this scale are: the ability to use telephone, to shop, to prepare food, to get along with the housekeeping, the laundry, to use the means of transportation, the responsibility for taking their own medication and to handle finances. The instrument is most useful for identifying how a person is functioning at the present time and for detecting changes over time. Administration time is 10-15 minutes. Many methods of grading

have been proposed and in the present study we will use multiple coding methods in order not to lose valuable information. Another drawback of the scale has been the "expected normal differences" in the IADL between the two genders and for that reason we intent to consider also the sex parameter when analysing the results. Despite some disadvantages, this scale is the maybe the most widely used in research and clinical setting.

Table 12 summarizes the components of this subset of the clinical assessment, whereas annexes 6 and 7 present the exact questionnaires. Translations of the two questionnaires exist in both Greek and French (22).

Table 12. ACTIVITIES OF DAILY LIVING

Activities of daily living	Katz Index of Independence of ADL (Annex 6)
Instrumental activities of daily living	Lawton IADL scale (Annex 7)

3.1.10 Assessment subset 10: Cognitive, mood and sleep evaluation

This session includes the following parts:

Global cognitive function evaluation. The Mini Mental State Examination (MMSE) test is employed (23), (annex 8), available in translated and validated versions in both French and Greek (24, 25). This scale is the most widely used instrument of global assessment of cognitive function both in clinical, epidemiological and research settings. It is useful as a screening tool in order to detect a cognitive dysfunction and to follow up its evolution, but it lacks specificity to distinguish between certain forms of dementia and sensitivity to discriminate a mild dysfunction in an early stage (26). Moreover it is highly influenced by the age and educational level (27, 28). A cut off score of below 24 during the first evaluation is used as an exclusion criterion for the present study, in order to avoid recruiting participants with important cognitive problems who are less likely to be able to use in an optimal way the FrailSafe system's devices and applications and to be apt for the follow up period.

To overcome the inherent inability of MMSE to detect more discreet cognitive dysfunctions and to augment the sensitivity of cognitive testing in highly educated older adults, the Montreal Cognitive Assessment (MoCA, annex 9) is also employed. The latter is a brief cognitive screening tool for the detection of MCI (29, 30, 31), available in multiple languages, among which the French and Greek. Since MCI is an important morbidity for our study, this scale will contribute to its detection.

- Memory complaint's detection. The expression of a memory complain from an older subject could be an indication of early sings of cognitive dysfunction (32), although there is not global consistency in this finding in the literature (33). Still, the general tendency is that subjective memory complains merit further evaluation (34, 35).
- Depression screening. The 15-items' Geriatric Depression Scale (GDS) (36) (annex10) is used in order to detect subjects with possible depression. This scale cannot pose the definitive diagnosis of depression, even though there is some evidence that it can detect a major depressive episode (37). Still it can be used to screen for depressive symptoms (38). It is available in both Greek in a validated version (39) and in French (40).
- Sleep problem. This pathology is investigated through questioning to the individual and also assessment of any special hypnotic treatment.

The sub questionnaire of this session is summarized in table 13 and annexes 8-10 contain the complete tests.

Table 13. CONGITIVE, MOOD AND SLEEP EVALUATION

Cognitive function	Scale MMSE (Mini Mental State Examination) (Annex 8)	
	Scale MoCA (Montreal Cognitive Assessment) (Annex 9)	
Memory complain	Question to the participant:	
	"Do you have the impression that your memory works less well in comparison to the people of your age?"	
	1. No	
	2. Yes	
Depression	Geriatric Depression Scale- 15 items (Annex 10)	
Sleep	Choose the one that applies	
	The need of medication to sleep correspond also in a sleep problem	
	1. No sleep problem	
	2. Occasional sleep problem	
	3. Permanent sleep problem	

3.1.11 Assessment subset **11**: Self-evaluation scales

The last session of the clinical evaluation battery aims at quantifying some subjective aspects of health perception and quality of life in general. It includes evaluation of:

- Health state: the person is asked to self-rate his/her health condition in respect to his/her age, giving a grade from 1 to 5, which corresponds to qualitative characterization of their health self-perception from very bad to excellent. Afterwards, a comparison to the past year is also requested. These two items are taken from the SF-36 questionnaire (41).
- Quality of life (QoL) self-rating: the question emphasizes the general aspect of QoL and not merely the "health related QoL". A visual analogue scale (VAS) in vertical orientation is employed and the person is asked to put a mark in the level that corresponds to his/her estimation.
- Pain self-evaluation: the assessment of pain is a central element of the evaluation of the older subject. Pain, which sometimes rests under-expressed, underdiagnosed and undertreated, can have devastating consequences in the physical and mental wellbeing of a person. A visual analogue scale (VAS) in vertical orientation is employed and the person is asked to put a mark in the level that corresponds to his/her estimation.
- Anxiety self-evaluation: A visual analogue scale (VAS) in vertical orientation is employed and the person is asked to put a mark in the level that corresponds to his/her estimation.

Both VAS (42, 43) and one-item self-rating evaluation systems (44, 45) have shown satisfying validity in personal perception measurements, even in older adults, comparable to those of more extended scales. Table 14 summarizes this subset of the battery and annexes 11-13 illustrate the actual VAS that are used.

Quality of life self-rating	Visual analogue scale (Annex 11)	
	"In generally, and not only referring to your health, how would you grade the quality of your life?"	
Health self-rating	"In generally and according to your age, how would you rate your health from 1 to 5, where 1 means very bad and 5 means excellent?"	
	Check the one that applies	
	1. Very bad	
	2. Bad	
	3. Medium	
	4. Good	
	5. Excellent	
	"Comparing to a year ago, how would you rate your health	

Table 14. SELF-EVALUATION SCALES

	now?"	
	Check the one that applies	
	1. A lot worse	
	2. A little worse	
	3. About the same	
	4. A little better	
	5. A lot better	
Pain self-evaluation	Visual analogue scale (Annex 12)	
	"Please mark on the line the point that you feel better represents your perception of your current state about pain."	
Anxiety self-evaluation	Visual analogue scale (Annex 13)	
	"Please mark on the line the point that you feel better represents your perception of your current state about anxiety."	

3.2 Data regarding social interaction and natural language analysis

An interesting aspect of the FrailSafe approach proposed is the text mining component that is based on the written scripts and the social interaction of the older adult using social media which will try to capture their personality and their current emotional state and possibly correlate (via machine learning approaches) the word usage and the social media behaviour of older adults to frailty symptoms. In order to proceed in this analysis natural language sentences need to be collected, personality traits need to be recognized and the social media interaction need to be explored.

